9.3. Joint Investigator/Sponsor Responsibilities

9.3.1. Payment Reporting

Investigators and their study staff may be asked to provide services performed under this protocol, e.g., attendance at Investigator's Meetings. If required under the applicable statutory and regulatory requirements, Gilead will capture and disclose to Federal and State agencies any expenses paid or reimbursed for such services, including any clinical trial payments, meal, travel expenses or reimbursements, consulting fees, and any other transfer of value.

9.3.2. Access to Information for Monitoring

In accordance with regulations and guidelines, the study monitor must have direct access to the investigator's source documentation in order to verify the accuracy of the data recorded in the eCRF.

The monitor is responsible for routine review of the eCRF at regular intervals throughout the study to verify adherence to the protocol and the completeness, consistency, and accuracy of the data being entered on them. The monitor should have access to any subject records needed to verify the entries on the eCRF. The investigator agrees to cooperate with the monitor to ensure that any problems detected through any type of monitoring (central, on site) are resolved.

9.3.3. Access to Information for Auditing or Inspections

Representatives of regulatory authorities or of Gilead may conduct inspections or audits of the clinical study. If the investigator is notified of an inspection by a regulatory authority the investigator agrees to notify the Gilead medical monitor immediately. The investigator agrees to provide to representatives of a regulatory agency or Gilead access to records, facilities, and personnel for the effective conduct of any inspection or audit.

9.3.4. Study Discontinuation

Both the sponsor and the investigator reserve the right to terminate the study at any time. Should this be necessary, both parties will arrange discontinuation procedures and notify the appropriate regulatory authority(ies), IRBs, and IECs. In terminating the study, Gilead and the investigator will assure that adequate consideration is given to the protection of the subjects' interests

Appendix 2. Study Procedures Table

EVENT		Screening ^a	Treatment Period												Follow-Up ^d
Visits	Day 1 ^b		W2	W4	W8	W12	W16	W20	W24	W30	W36	W44	W52/ ET ^c	Post Treatment Week 4	
Visit window (Days)	(±3 days)		(±3 days)	(±3 days)	(±3 days)	(±3 days)	(±3 days)	(±3 days)	(±3 days)	(±3 days)	(±7 days)	(±7 days)	(±7 days)	(±7 days)	(±7 days)
Screening Assessments	Informed Consent	X													
	Inclusion/Exclusion Criteria	X	X ^e												
	Demographics and Baseline Disease Characteristics	X													
	RA diagnosis and Prior RA Treatment, Medical History ^f	X													
	Complete Physical Examination ^g	X							X				X		
	TB test and Chest X-Ray ^h	X													
	RF/anti-CCP Ab	X													

EVENT		Screening ^a	Treatment Period												Follow-Up ^d
			Day 1 ^b	W2	W4	W8	W12	W16	W20	W24	W30	W36	W44	W52/ ET ^c	Post Treatment Week 4
Visits	Visit window (Days)			(±3 days)	(±3 days)	(±3 days)	(±3 days)	(±3 days)	(±3 days)	(±3 days)	(±7 days)	(±7 days)	(±7 days)	(±7 days)	(±7 days)
Patient Questionnaires	Subject's global assessment ⁱ	X	X	X	X	X	X	X	X	X	X	X	X	X	
	HAQ-DI and Pain Scale ⁱ	X	X	X	X	X	X	X	X	X	X	X	X	X	
	FACIT-Fatigue, SF-36, WPAI-RA, EQ-5D ¹		X		X		X			X		X		X	
	Healthcare Resource Utilization Questionnaire and TSQM ¹		X				X			X		X		X	
CCI															
Physical Exam and Provider Assessments	Physician's global assessment	X	X	X	X	X	X	X	X	X	X	X	X	X	
	Vital signs ^j	X	X	X	X	X	X	X	X	X	X	X	X	X	X
	Symptom-driven physical examination		X	X	X	X	X	X	X		X	X	X		X
	12-Lead ECG	X				X			X		X		X		X
	SJC66/TJC68	X	X	X	X	X	X	X	X	X	X	X	X	X	
	Weight	X	X	X	X	X	X	X	X	X	X	X	X	X	X

EVENT		Screening ^a	Treatment Period												Follow-Up ^d
Visits	Day 1 ^b		W2	W4	W8	W12	W16	W20	W24	W30	W36	W44	W52/ ET ^c	Post Treatment Week 4	
Visit window (Days)			(±3 days)	(±3 days)	(±3 days)	(±3 days)	(±3 days)	(±3 days)	(±3 days)	(±7 days)	(±7 days)	(±7 days)	(±7 days)	(±7 days)	
Laboratory Assessments	Pregnancy test ^k	X	X	X	X	X	X	X	X	X	X	X	X	X	
	Hematology and Chemistry ^l	X	X	X	X	X	X	X	X	X	X	X	X	X	
	Serum CRP	X	X	X	X	X	X	X	X	X	X	X	X		
	Urinalysis and urine for biomarkers ^m	X	X				X			X				X	
	Quantitative IG	X							X				X		
	Endocrine: FSH, TSH, and HbA1c	X													
	Lipid profile (fasting) ^l		X				X		X				X		
	CCI														
	PK blood samples ^o				X		X			X				X	
	Biomarker Blood Samples: Plasma biomarker, serum biomarker, transcriptome, TCR/BCR repertoire ^p		X		X	X	X			X		X		X	
	vfPBMC and Leukocyte subset ^q		X		X	X	X			X		X		X	
Serology	X ^r														
Viral Monitoring ^s						X			X		X		X		

[figure not shown]
EVENT		Screening ^a	Treatment Period											Follow-Up ^d	
Visits			Day 1 ^b	W2	W4	W8	W12	W16	W20	W24	W30	W36	W44	W52/ ET ^c	Post Treatment Week 4
Visit window (Days)				(±3 days)	(±3 days)	(±3 days)	(±3 days)	(±3 days)	(±3 days)	(±3 days)	(±7 days)	(±7 days)	(±7 days)	(±7 days)	(±7 days)
Imaging ^e	Hand, Wrist and Feet Radiographs ^t	X							X				X		
	CCI														
Assessment of Adverse Events		X	X	X	X	X	X	X	X	X	X	X	X	X	
Concomitant Medications		X	X	X	X	X	X	X	X	X	X	X	X	X	
Randomization/reassignment			X						X ^v		X ^w	X ^w	X ^w		
Study Drugs Dispensation ^x			X		X	X	X	X	X	X	X	X			
Review entry criteria for LTE (if applicable)													X		

Footnotes

- a Screening window is 28 days prior to Day 1, the window may be extended to up to 42 days prior to the Day 1 visit for subjects who require repeat collection of radiographs
- b Subject will begin study drugs on Day 1, following baseline assessments and randomization.
- c Early Termination Visit to be performed if subject discontinues before Week 52
- d The follow-up visit will be performed only for subjects discontinuing prematurely from the study and for those completing Week 52 but not entering the LTE.
- e Eligibility criteria check based on the laboratory results from the Screening visit, TJC/SJC at screening and Day 1 and for female subjects of childbearing potential, the urine pregnancy test at Day 1.
- f Medical History includes smoking status, average weekly alcohol consumption, family history of coronary heart disease and any other chronic medical conditions or prior surgeries
- g At Screening, Week 24 and Week 52 (or at ET), a complete physical should be performed. Symptom driven exams should be performed at all other visits. Height will be measured at Screening only.
- h Chest X-ray for TB assessment should be performed unless performed in the previous 3 months, with results available at the site.
- i Subject reported outcomes are recommended to be performed first at each visit prior to any other visit-related procedures (other than signing of informed consent), as much as possible. Questionnaire translations will be provided to subjects when and where available.
- j Vital signs are defined as heart rate, respiratory rate, blood pressure (systolic and diastolic) and body temperature.

- k For female subjects of childbearing potential only. To be performed on serum sample at Screening and on urine samples for other visits. For female subjects entering the LTE, at the Week 52 visit pregnancy test should be performed on serum. During the periods where visits are every 6-8 weeks, women should continue to have monthly home pregnancy tests performed at home. The site will call the subject every 4 weeks to obtain results of these pregnancy tests. If any pregnancy test is positive, study drug should be immediately interrupted and subject should come to the site for serum pregnancy test.
- l Refer to list provided in Laboratory assessment table ([Appendix 6](#)).
- m Urine samples for biomarker analysis should be collected at Day 1, Weeks 12, 24, and Week 52 or ET
[REDACTED]
- n The PK sample at Week 4 should be collected at least 30 minutes post study drug dose in the clinic. PK samples at Week 12 and Week 24 should be collected prior to study drug dose (within 2 hours prior to dosing). The PK sample at Week 52 or ET can be collected at any time during the visit. **CCI**
[REDACTED]
- p Details of biomarker collection are outlined in lab manual
- q Only for subjects in United States and Canada
- r Hepatitis B surface Ag and core Ab, reflex Hep B DNA, Hepatitis C Ab, reflex HCV RNA, HIV 1 and 2 at Screening.
- s Viral monitoring for HBV or HCV as applicable (see Exclusion criteria, Section 4.3).
- t Radiographs performed after enrollment may be done +/- 7 days of the scheduled visit. If subject discontinues study early and has had x-rays in the <12 weeks prior, x-rays do not need to be repeated at the ET visit.
[REDACTED]
- v Subjects failing to achieve at least a 20% improvement from Day 1 in TJC and SJC will discontinue study drugs, but will continue with study visits and assessments
- w Subjects failing to maintain at least a 20% improvement from Day 1 in TJC and SJC (confirmed at 2 consecutive visits) will discontinue study drugs, but will continue with study visits and assessments
- x Dispensation of study drugs according to IWRS manual.

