For a complete list of study inclusion and exclusion criteria, please refer to Sections 4.2 and 4.3.

Main Eligibility Criteria

- 1) Male or female subjects who are ≥18 years of age, on the day of signing informed consent
- 2) Have a diagnosis of RA (2010 ACR/ EULAR criteria), and are ACR functional class I-III
- 3) Have ≥6 swollen joints (from a SJC66) and ≥6 tender joints (from a TJC68) at Screening and Day 1

- 4) Must meet at least one of the following parameters at Screening:
 - positivity for either RF or anti-CCP Ab per central laboratory
 - OR
 - Serum CRP \geq 4 mg/L based on central laboratory value
 - OR
 - \geq 1 documented joint erosion on radiographs of the hands, wrists or feet by central reading
- 5) Limited or no prior treatment with MTX, ie, no more than 3 doses of MTX \leq 25 mg each in their lifetime for the treatment of RA, with last dose at least 28 days prior to Day 1, and are an appropriate candidate for MTX therapy, as per investigator judgment

Study Procedures/
Frequency:

The subjects will visit the clinical study center at Screening, Day 1, Weeks 2, 4, 8, 12, 16, 20, 24, 30, 36, 44, and 52 or ET.

For those subjects not entering the LTE, a follow-up visit will be planned 4 weeks after the last dose of study drug (Post Treatment Week 4). Consequently, subjects are planned to be in the study for approximately 60 weeks.

During the Screening period, the subject's radiographs (hands, wrists, and feet) will be sent for blinded central scoring. In addition, information on demographics, medical history/concomitant diseases, prior and current RA medications will be collected. A physical examination, a 12-lead electrocardiogram (ECG), and clinical laboratory assessments will be conducted to determine the subject's eligibility for study participation. The screening window may be extended to up to 42 days prior to the Day 1 visit for subjects who require repeat collection of radiographs only.

At Day 1, after the subject's eligibility for the study has been confirmed, the subject will be randomized to receive one of 4 dosing regimens: filgotinib 200 mg q.d. plus MTX up to 20 mg weekly, filgotinib 100 mg q.d. plus MTX up to 20 mg weekly, filgotinib monotherapy 200 mg q.d. or MTX monotherapy up to 20 mg weekly.

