3.7. Post Study Care

All subjects who meet criteria for clinical response (per protocol), and who complete 52 weeks of study assessments will be offered an opportunity to participate in a LTE study (GS-US-417-0304). Subjects who discontinue early from the main study, or switch to standard of care treatment during the study, are not eligible for the LTE. The long term care of subjects who do not qualify for the LTE or choose not to participate in the LTE will remain the responsibility of their primary treating physician.

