6.5. Week 52/Early Termination (ET)

If a subject discontinues the study, every attempt should be made to perform the required study-related ET and Post Treatment Week 4 visits and procedures.

Subject's Global Assessment, HAQ-DI and Pain Scale, FACIT- Fatigue, and SF-36 are recommended to be done before any other study procedures. Invasive study procedures such as blood draws should be done at the end of a study visit.

- Subject's global assessment
- HAQ-DI and Pain Scale
- FACIT-Fatigue and SF-36,
- WPAI-RA and EQ-5D, where available

- TSQM, when and where available
- Healthcare resource utilization questionnaire
- Complete physical examination
- Weight
- Vital signs
- SJC66/TJC68
- Physician's global assessment
- 12-Lead ECG
- Radiographs of hands, wrists, and feet

- Obtain blood samples for:
 - Hematology and Serum Chemistry
 - Lipid profile (fasting)
 - Serum CRP
 - Pregnancy test (serum required if subject is entering into LTE)
 - Blood sampling for PK
 - Biomarker blood samples
 - Quantitative Ig
 - vfpBMC and leukocyte subset samples (US and Canada only)
- Urinalysis (including pregnancy test if applicable)
- Urine stored for biomarker analysis
- Assessment of AE(s)/serious (S)AE(s) and concomitant medication
- Review Entry criteria for LTE (if applicable)

6.6. Post Treatment Week 4

The following procedures will be completed 4 weeks after the subject's last dose of study treatment. This visit is not applicable if the subject is continuing onto the LTE study.

- Symptom-driven physical examination
- Weight
- Vital signs
- Urinalysis (including pregnancy test if applicable)
- 12-lead ECG
- Obtain blood samples for:
 - Hematology and Serum Chemistry
- Urinalysis
- Assessment of AE(s)/SAE(s) and concomitant medication

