**Table 3-6. Analysis Visit Windows for On-Treatment HRUQ and TSQM**

Analysis Visit	Nominal Study Day	Lower Limit	Upper Limit
Baseline	1	(none)	1
Week 12	85	2	127
Week 24	169	128	211
Week 36	253	212	309
Week 52	365	310	≥ 365

Vital signs, weight, ECGs, lipids, and safety laboratory data collected in the posttreatment followup period will also be summarized. The analysis window for posttreatment followup period is defined as from (the last dose date of any study drug + 8 days) to (the last dose date of any study drug + 30 days). If multiple valid, nonmissing measurements exist in the posttreatment followup visit window, then the latest record will be selected for analysis. If the chronological order cannot be determined (eg, more than 1 record on the same day with time missing), for any given subject, the value with the worst severity will be selected for categorical variable, and the average will be taken for continuous variable. Data obtained after last dose date plus 30 days will be excluded from the summaries, but will be included in the listings.

For efficacy endpoints, the same analysis visit windows will be applied to all available data collected during standard of care.

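### Appendix 2 footnote d and Section 6.6 disagree on when subjects who stop drug but stay in the study have the Post Treatment Week 4 visit, and the SAP's 30-day cut-off is shorter than that visit's own window

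*Protocol*

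**What the plan says.** **Who has the visit.** Protocol Appendix 2, footnote d: "The follow-up visit will be performed only for subjects discontinuing prematurely from the study and for those completing Week 52". The footnote limits the second of these groups to completers who do not go on to the LTE.

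**When it takes place.** Section 6.6 opens with "The following procedures will be completed 4 weeks after the" last dose, and gives one exception: "This visit is not applicable if the subject is continuing onto the LTE study". For subjects not entering the LTE, the synopsis says "a follow-up visit will be planned 4 weeks after the last dose of study drug (Post Treatment Week 4"). Section 3.2 also gives the visit to every subject not entering the LTE.

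**The group in question.** Subjects who fail the 20% joint-count rule at Week 24, or lose response at two consecutive visits from Week 30, "will discontinue study drugs, but will continue with study visits and assessments" (Appendix 2, footnotes v and w; also the synopsis and Section 3.2). Section 3.7 adds that subjects who leave early or "switch to standard of care treatment during the study, are not eligible for the LTE".

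**What the SAP summarises.** Section 3.8.2 ends the on-treatment period at last dose +7 days and runs the post-treatment window from last dose +8 to +30 days. It applies to vital signs, weight, ECGs, lipids and safety laboratory data. Beyond that, "Data obtained after last dose date plus 30 days will be excluded from the summaries"; such data appear in listings only. The laboratory summaries, graded abnormalities, and liver and blood-count tables in SAP Section 7.2 also stop at last dose +30 days. The Post Treatment Week 4 visit itself carries a ±7-day window in Appendix 2.

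**The concern.** The footnote is triggered by leaving the study or reaching Week 52; Section 6.6 is triggered by the last dose. For most subjects the two coincide. They separate for subjects who come off drug by rule and stay on the visit schedule. These subjects have not left the study and have not yet completed Week 52, so a site working from the procedures table has no instruction to see them 4 weeks after last dose. A site working from Section 6.6 does. With 200–250 planned centres, practice is likely to be uneven.

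At stake are the off-drug measurements the protocol itself treats as safety signals: neutrophils, platelets, transaminases and creatinine, together with vital signs, weight and ECG. Subjects enter this group through non-response, so its size may differ between arms. If their first off-drug measurement falls after the SAP cut-off, the group contributes nothing to the post-treatment tables.

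The cut-off raises a second issue that does not depend on the footnote. A visit that the protocol accepts as on time can still be too late for the SAP.

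**Working it through.** **1. Visit days.** SAP Section 4.2.1 gives nominal days 169, 211, 253, 309 and 365 for Weeks 24, 30, 36, 44 and 52. All five reproduce as 7 × week + 1.

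**2. Visit windows (Appendix 2).** ±3 days at Week 24; ±7 days from Week 30 onward and at Post Treatment Week 4.

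**3. Possible stop visits.** Week 24 by the non-response rule. Loss of response needs two consecutive visits from Week 30, so the earliest such stop is Week 36, then Week 44 or 52.

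**4. Gap to the next scheduled visit.** Gap = difference in nominal days; range = gap ± the sum of the two windows. The last dose is taken to be on the day of the stop visit (assumption).

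| Stop | Next visit | Nominal gap | Range |
|---|---|---|---|
| Week 24 | Week 30 | 211 − 169 = 42 days | 42 ± (3+7) = 32–52 |
| Week 36 | Week 44 | 309 − 253 = 56 days | 56 ± (7+7) = 42–70 |
| Week 44 | Week 52 | 365 − 309 = 56 days | 56 ± (7+7) = 42–70 |

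Even the shortest gap, 32 days, is past last dose +30. It is past by only 2 days, so the result at that extreme depends on the assumption about last dose. An earlier last dose lengthens the gap and a later one shortens it.

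**5. ECG.** Protocol Section 6.4 schedules ECGs at Weeks 12, 24 and 36, and Section 6.5 at Week 52; none is due at Week 30 or 44. The first off-drug ECG on the ordinary schedule is therefore later still after two of the stops: 253 − 169 = 84 days after a Week 24 stop and 365 − 253 = 112 days after a Week 36 stop.

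**6. If the footnote is taken to mean 4 weeks after Week 52.** That visit is at Day 365 + 28 = 393, which is 224 days (32 weeks) after a Week 24 stop, 140 days after Week 36 and 84 days after Week 44. All lie outside the SAP window.

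**7. If Section 6.6 is followed.** The visit falls at Day 28 ± 7, that is Days 21–35 after last dose. Days 31–35, 5 of the 15 permitted days, are beyond the SAP cut-off. This holds for every subject who has the visit, whichever passage governs.

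**8. Exceptions.** A subject stopped at Week 52 is covered by the footnote at Days 21–35. A subject who missed Week 24 and was stopped at Week 30 has a nominal gap of 253 − 211 = 42 days to Week 36, but it could be as short as 42 − 14 = 28.

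**The case against.** The strongest reply is that the passages can be read together. Footnote d says who has the visit, not when; timing comes from Section 6.6 and the synopsis, which count from last dose. Subjects stopped by the rule cannot enter the LTE, so each either leaves early or completes Week 52 outside the LTE, and the footnote names both groups. On that reading they have a visit at about Day 28. This is a fair reading, and it rules out two stronger inferences: that these subjects have no post-treatment visit at all, and that the protocol places it 32 weeks after their last dose. It does not remove the conflict. The footnote says the visit is done only for those two groups, and a subject who stopped drug at Week 24 belongs to neither until leaving the study or reaching Week 52.

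A reader might also infer that off-drug safety goes unobserved in this group. The documents do not support that:

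- Adverse events are collected to 30 days after last dose (Protocol Section 7.3) and counted as treatment-emergent by onset date (SAP Section 7.1.5.1), so those recorded at a later visit still count.
- Pregnancy tests continue every 4 weeks through 35 days after last dose, with home kits (Protocol Appendix 5).
- Haematology and chemistry are drawn at Weeks 30, 36, 44 and 52, and late values are listed.

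What is lost is the entry of visit-based measurements into the summary tables.

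Finally, the 30-day limit is not an SAP oversight. Protocol Section 8.6 sets it as the default for safety data and the adverse-event rules share it. That stands as a reason to leave the adverse-event definition alone. It does not explain a cut-off shorter than the visit it is meant to capture, and Section 8.6 allows other limits where specified.

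**Conclusion.** The point holds as an inconsistency plus a mismatch of windows. Footnote d and Section 6.6 (with the synopsis and Section 3.2) give different answers for subjects stopped at Week 24, 36 or 44 who remain in the study. Where footnote d is followed, their next scheduled visit is 32–52 or 42–70 days after the stop visit, beyond the SAP's summaries, given a last dose on the day of the stop visit. Independently, in-window visits on Days 31–35 are left out of the summaries. The 5-in-15 figure counts permitted days; it is not an estimate of the share of visits lost.

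It would be too strong to say that none of these subjects can have an assessment inside the SAP window, given the Week 52 and Week 30 exceptions above.

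The documents do not give the number affected. As an assumption only, 5%, 10% or 20% of 1200 subjects would be 60, 120 or 240. The planning ACR20 rates of 62% and 78% imply 38% and 22% non-response. That is a loose ceiling for the Week 24 rule, because ACR20 also needs three of five other items and counts missing data as failure. The change should be made, but nothing here touches the efficacy conclusions.

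**What to change.** **Protocol.** Reconcile Appendix 2 footnote d with Sections 3.2 and 6.6 and the synopsis, so that one statement says whether and when subjects who stop drug but stay in the study have the Post Treatment Week 4 visit. Which passage governs is for the sponsor to decide.

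**SAP.** Extend the post-treatment window for visit-based measures in Section 3.8.2, and the laboratory cut-offs in Section 7.2, from last dose +30 to last dose +35 days. Keep the 30-day definition of treatment-emergent adverse events. Section 3.8.2 takes the latest record in the window, so a Week 30 visit made 32–35 days after a Week 24 stop could then displace the Post Treatment Week 4 record; state that the latter takes precedence where it exists.

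**Cost.** Wording changes in both documents, plus one short visit, already described in Section 6.6, if that section is taken to govern. Laboratory and vital-sign data would have a slightly longer post-treatment period than adverse events. That departs from the Protocol Section 8.6 default and should be recorded in SAP Section 7.7, which now reports no deviations.

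A separate table of the first off-drug visit is optional. These subjects are to receive standard-of-care treatment, so values 42–56 days later would mix the effect of stopping study drug with that of new therapy.
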